### 1. INTRODUCTION

This statistical analysis plan (SAP) is based on the Protocol # GC2010 Version 5.0, dated 13 October, 2021, and titled "A Multicenter, Randomized, Double-blind, Parallel Group Study to Evaluate the Safety and Efficacy of Anti-COVID-19 Immune Globulin (Human) 20% (C19-IG 20%) versus Placebo in Asymptomatic Ambulatory Outpatients with Severe Acute Respiratory Syndrome Coronavirus 2 (SARS-CoV-2) Infection." See the study protocol for full details.

This document details the statistical methods planned to perform the Data Safety Monitoring Board (DSMB), interim futility and final analyses of the study.

### 2. OBJECTIVES AND ENDPOINTS

#### 2.1 Objectives

#### 2.1.1 Primary Efficacy Objective

To compare C19-IG 20% (2 doses) versus Placebo with regard to proportion of asymptomatic subjects who remain asymptomatic, i.e., who do not develop symptomatic coronavirus disease 2019 (COVID-19) through Day 14 defined as any of the following:

Experiencing at least TWO of the following systemic symptoms: (a) Fever ( $\geq$  38°C), (b) chills, (c) myalgia, (d) headache, (e) sore throat, (f) cough, (g) fatigue that interferes with activities of daily living, (h) new olfactory and taste disorder(s), (i) vomiting/diarrhea (note that [h] new olfactory/taste disorder(s) & [i] vomiting/diarrhea Each Only count as ONE item of definition)

OR

Experiencing at least ONE of the following respiratory signs/symptoms: new or worsening shortness of breath or difficulty breathing,

OR

Experiencing peripheral oxygen saturation by pulse oximetry (SpO2) < 94% on room air

OR

Radiographical evidence of pneumonia (radiographic infiltrates by imaging [chest X-Ray, CT scan, etc.]). Note radiographical studies are to be done for suspicion of pneumonia per standard of care

#### 2.1.2 Secondary Efficacy Objectives

- To compare C19-IG 20% (2 doses) versus Placebo with regard to change in SARS-CoV-2 viral load (log10 copies/mL) from Baseline (Day 1) to Day 7 and to Day 14.
- To compare C19-IG 20% (2 doses) versus Placebo with regard to proportion of subjects who remain in an outpatient setting and maintain SpO2 ≥94% on room air on Day 3, Day 7, and Day 14.
- To compare C19-IG 20% (2 doses) versus Placebo with regard to proportion of subjects negative and time to negative SARS-Cov-2 by polymerase chain reaction (PCR) from

Baseline through Day 14 and through Day 29.

- To compare C19-IG 20% (2 doses) versus Placebo with regard to clinical efficacy in asymptomatic ambulatory outpatients as assessed by clinical evolution to overt COVID-19, new dependency on oxygen and if needed duration of oxygen supplementation, clinical response criteria including National Early Warning Score (NEWS) and ordinal clinical status scale through Day 29.
- To compare C19-IG 20% (2 doses) versus Placebo with regard to frequency of requirement for hospital-level medical care (i.e., hospitalization admission defined by need for medical intervention[s], not for quarantine purposes) and duration of hospitalization (if required) through Day 29.
- To compare C19-IG 20% (2 doses) versus Placebo with regard to proportion of asymptomatic subjects with COVID-19 who require at least one COVID-19 related medically attended visit for management/treatment of COVID-19 (apart from routinely scheduled study-directed visits) which may occur in any setting through Day 29 (e.g., Emergency department, urgent care, outpatient clinic or professional setting wherein direct in-person/telemedicine medical assessment and escalation of care for COVID-19 is provided by licensed healthcare personnel).

### 2.1.3 Exploratory Efficacy Objectives

The exploratory objectives of the study are:

- To evaluate the effect of C19-IG 20% (2 doses) versus Placebo with regard to change from baseline in inflammatory biomarkers specifically: interleukin 6 (IL-6); D-dimer; ferritin; C-reactive protein (CRP), and interferon γ through Day 14.
- To evaluate the effect of C19-IG 20% (2 doses) versus Placebo with regard to quantitative anti-SARS-CoV-2 antibodies through Day 14.
- Overall assessment of COVID-19 symptoms severity on Day 7 and Day 29.

### 2.1.4 Safety Objective

- To determine the safety and tolerability profile of C19-IG 20% (2 doses) versus Placebo through Day 29.
- To evaluate change from baseline in key biochemical parameters of organ function/dysfunction: alanine aminotransferase (ALT); lactate dehydrogenase (LDH); absolute lymphocyte count; creatinine through Day 14.

### 2.2 Endpoints

### 2.2.1 Primary Efficacy Endpoint

The primary efficacy endpoint is the proportion of asymptomatic subjects who remain asymptomatic. See details above in Section 2.1.1.

### 2.2.2 Secondary Efficacy Endpoints

The secondary efficacy endpoints include the following:

- Change in SARS-CoV-2 viral load (log10 copies/mL) from Baseline (Day 1) to Day 7 and to Day 14.
- Proportion of subjects who remain in an outpatient setting and maintain SpO2 ≥94% on room air on Day 3, Day 7, and Day 14.
- Proportion of subjects negative for SARS-CoV-2 by PCR at multiple time points through Day 14 and through Day 29.
- Time to negative SARS-CoV-2 PCR from Baseline through Day 29.
- Proportion of subjects who require O2 supplementation on or before Day 29.
- If requiring supplemental oxygen post randomization: Duration of any oxygen through Day 29.
- Absolute value and mean change from baseline in the 7-point Ordinal scale Day 1, Day 7, Day 14, and Day 29:

The 7-point Ordinal scale is as follows:

1) Death;

- 2) Hospitalized, on invasive mechanical ventilation or extracorporeal membrane oxygenation (ECMO);
- 3) Hospitalized, on non-invasive ventilation or high flow oxygen devices;
- 4) Hospitalized, requiring supplemental oxygen;
- 5) Hospitalized, not requiring supplemental oxygen;
- 6) Not hospitalized, limitation on activities;
- 7) Not hospitalized, no limitations on activities.
- Proportion (percentage) of subjects in each severity category of the 7-point Ordinal scale at Day 1, Day 7, Day 14, and Day 29.
- Assessment of Clinical Severity: Change in NEWS from baseline (at Day 7, Day 14, and Day 29).

The NEWS has demonstrated an ability to discriminate patients at risk of poor outcomes. This score is based on 7 clinical parameters (respiration rate, oxygen saturation, any supplemental oxygen, temperature, systolic blood pressure, heart rate, level of consciousness [Alert, Voice, Pain, Unresponsive]).

- Proportion of subjects who require at least one COVID-19 related medically attended visit for management/treatment of COVID-19 (apart from routinely scheduled study-directed visits) which may occur in any setting through Day 29 (e.g., Emergency department, urgent care, outpatient clinic or professional setting wherein direct in-person/telemedicine medical assessment and escalation of care for COVID-19 is provided by licensed healthcare personnel).
- Proportion of subjects who require hospital admission for medical care (non-quarantine purpose) through Day 29.

- If admitted to hospital post randomization: Duration of hospital stay through Day 29.
- Proportion of subjects who require ICU admission or initiation of ICU-level care\* through Day 29.
- If admitted to ICU post randomization: Duration of ICU stay through Day 29.
- Proportion of subjects requiring invasive mechanical ventilation through Day 29.
- If requiring invasive mechanical ventilation post randomization: Duration of invasive mechanical ventilation through Day 29
- All-cause mortality through Day 29.
- Incidence of critical COVID-19 illness, defined as any one of the following: (a) requiring ICU admission or ICU level of care\*, (b) invasive mechanical ventilation, or (c) resulting in death by Day 29.
- Length of time to clinical progression to critical COVID-19 illness through Day 29 (defined as the time to death, invasive mechanical ventilation, or ICU admission/requiring ICU level of care).
- Time to COVID-19 symptoms specifically defined as the time to fulfillment of the case definition used for the primary efficacy variable through Day 14.

[\*Note: ICU level care is defined as the medical need for intensive or invasive monitoring; immediate or impending need for the support of the airway, breathing, or circulation; and/or stabilization of acute severe or life-threatening complications of COVID-19]

#### 2.2.3 Exploratory Efficacy Endpoints

The exploratory efficacy endpoints include:

- Change from baseline in inflammatory biomarkers specifically: IL-6; D-dimer; ferritin; CRP; interferon γ through Day 14.
- Change from baseline in quantitative anti-SARS-CoV-2 IgM and IgG antibodies through Day 14.
- Overall assessment of COVID-19 symptoms severity (No symptoms; Mild; Moderate; Severe; Potentially Life-threatening) on Day 7 and Day 29.

#### 2.2.4 Safety Endpoints

The safety endpoints include:

- Cumulative incidence of treatment-emergent serious adverse events (SAEs) and potentially related SAEs through Day 60 Phone Check.
- Cumulative incidence of Grade 3-5 treatment-emergent adverse events (TEAEs) and potentially related severe TEAEs through Day 29 as defined in the Common terminology Criteria for Adverse Events (CTCAE), US Department of Health and Human Services, National Institutes of Health (NIH), and National Cancer Institute (NCI) through Day 29.

- Cumulative incidence of all TEAEs and potentially related TEAEs through Day 29.
- Change from baseline in key biochemical parameters of organ function/dysfunction: ALT; LDH; absolute lymphocyte count; creatinine through Day 14.

# 3. INVESTIGATIONAL PLAN

## 3.1 Study Design

This is a prospective, multi-center, randomized (1:1:1), double-blind study of C19-IG 20% at 1 of 2 dose levels versus Placebo in asymptomatic, ambulatory outpatients aged  $\geq$ 18 years who are SARS-CoV-2 positive. Participants will be stratified by age <65 years vs  $\geq$ 65 years of age. The study will enroll asymptomatic subjects with laboratory-confirmed novel coronavirus (SARS-CoV-2) infection as determined by qualitative PCR (reverse transcriptase [RT]-PCR), or other commercial or public health assay approved by regulatory authorities as a diagnostic for COVID-19 (inclusive of SARS-CoV-2 antigen testing or other approved rapid testing platforms) in any specimen obtained  $\leq$  5 days prior to randomized treatment ( $\leq$  5 days is the post-sampling timeframe from date specimen obtained to administration of blinded study drug). Every effort should be made to reduce this time interval to the minimum as nearly immediate treatment is key for successful intervention.

Approximately 801 subjects (267 per arm) will be randomized (1:1:1). Subjects randomized to C19-IG 20% will receive a blinded subcutaneous (SC) infusion on Day 1 at a dose of either 1 gram or 2 grams, according to the randomized dose assigned. Subjects randomized to Placebo will receive a SC infusion of sterile 0.9% sodium chloride injection, United States Pharmacopeia (0.9% NaCl, USP) or equivalent. Blinded study drug will be prepared and administered by an unblinded study nurse who is entirely independent of the evaluating study team with SC infusions using 2 separate syringes as follows:

- Placebo (*two* syringes each containing 5 mL 0.9% NaCl);
- 1 gram C19-IG 20% (one syringe containing 5 mL C19-IG 20% *Plus* one syringe containing 5 mL 0.9% NaCl)
- 2 grams C19-IG 20% (*two* syringes each containing 5 mL C19-IG 20%).

An independent DSMB will review interim safety data when approximately 399 patients have been randomized and treated with follow-up through Day 29 (approximately 133 patients per randomized group).

Subjects will receive one C19-IG 20%/Placebo dose via SC route on Day 1; for all subjects monitoring and surveillance will be continued throughout the subject's participation in the study. The total estimated maximum duration of a subject's participation in terms of actual Healthcare Provider Visits will be up to 30 days. Additionally, a Phone Check will occur at Day 60 for complete follow-up. Thus, subject participation (from Screening Visit to the Final Phone Check) will be approximately 60 days.

[figure not shown]
At the Healthcare Provider visit on Day 1, all subjects will receive a pulse oximeter for home use and daily recording of SpO2 in order to monitor for development of hypoxia (SpO2 < 94% on room air). All subjects will also be instructed to measure, monitor, and record body temperature daily. Subjects will be evaluated at Healthcare Provider Visits on Day 3, Day 7, Day 14, and Day

29 (or if hospitalized, assessments required for Day 7, Day 14, and Day 29 will be performed in hospital).

Additionally, subjects will be assessed as outpatients by Phone Check on Day 5, Day 9, and Day 11. The Phone Checks serve as surveillance for development of symptomatic COVID-19, sentinel alarm symptoms or symptoms that may indicate clinical deterioration (e.g., dyspnea) and to record the patient's daily entries for SpO2 and body temperature.

Following the Day 29 assessment time point, one more final Phone Check will be performed at Day 60 for vital status (living or deceased), any hospital admissions, ICU admissions, requirement for invasive mechanical ventilation, need for oxygen supplementation, or serious/non-serious adverse events after the Day 29 Healthcare Provider Visit, and to confirm resolution of any COVID-19 sequelae. See Appendix A for the Schedule of Events.

An overview of the study design is presented below:

Note: All subjects will receive a pulse oximeter for home use and daily recording of SpO2 in order to monitor for development of hypoxia (SpO2  $\leq$  94% on room air). All subjects will also be instructed to measure, monitor, and record body temperature daily. For single dose administrations all doses will be given in 2 syringes to maintain the blind. Note that given the pandemic setting it is likely that Healthcare Provider Visits may consist either of evaluations at the subject's usual residence (home) justified because subject is in confinement or at an alternate site, e.g., Clinic, always under the care and supervision of trained healthcare personnel.

# 3.2 Treatment

### 3.2.1 Randomization Scheme and Treatment Arm Assignment

Eligible subjects will be randomized 1:1:1 to Placebo or to C19-IG 20% via a SC infusion on Day 1 at a dose of either 1 gram or 2 grams, according to the randomized dose assigned. A central randomization stratified by age group (age <65 years versus  $\geq$  65 years) will be used for this study. Randomization will be centralized and will be performed via an Interactive Web Response System after subject inclusion. A randomization list containing the randomization numbers and the corresponding randomized treatment assignments will be generated and stored in a secured area that is only accessible to the randomization team.

### 3.2.2 Blinding

There will be a designated unblinded study nurse for preparation and administration of study drug who is entirely independent of the team evaluating the patient with SC infusions using 2 separate syringes as described above in Section 3.1.

The designated unblinded study nurse will be the only unblinded study person at each site. Preparation of study drug (Anti-COVID-19 Immune Globulin [Human] and placebo) and SC administration of study drug will be the responsibility of the local unblinded study nurse.

Since this is a double-blind, placebo-controlled study, measures will be taken to assure that the

CONFIDENTIAL

placebo infusion will be indistinguishable in terms of commensurate volume from Anti-COVID-19 Immune Globulin (Human) infusion volume to that required for the appropriate dose of Anti-COVID-19 Immune Globulin (Human) to maintain blinding. For all 3 arms a 10-mL volume (2 syringes each containing 5 mL volumes of various composition) will be prepared so that there is no difference in infusion volume or apparent configuration.

Furthermore, results of the central laboratory analysis of quantitative viral load and quantitative IgM and IgG anti-SARS-CoV-2 antibodies will not be shared with the Investigator, blinded study staff, clinical research organization or blinded Sponsor personnel involved in study conduct.

# 3.2.3 Dosing Schedule

Subjects randomized to C19-IG 20% will receive a blinded single dose via SC infusion of C19-IG 20%. Randomization to active treatment arms will specify either a dose of 1 gram or 2 grams C19-IG 20%. Subjects randomized to Placebo will receive blinded sterile 0.9% sodium chloride injection United States Pharmacopeia (0.9% NaCl, USP) or equivalent. Blinded study drug will be prepared and administered by an unblinded study nurse who is entirely independent of the evaluating study team with SC infusions using 2 separate syringes as described above in Section 3.1.

### **3.2.4** Treatment Compliance

Reasons for any deviation from the administration of less than 100% of the blinded investigational product (IP) dose must be recorded in the subject's medical records.

The investigator or designee is responsible for maintaining accurate records of C19-IG 20%/Placebo administered at his/her study center.

# 4. GENERAL CONSIDERATIONS FOR DATA ANALYSIS

Unless otherwise specified, continuous variables will be summarized using descriptive statistics (n, mean, standard deviation, median, minimum, and maximum). Categorical variables will be summarized showing the number and percentage of subjects within each category.

Summary results will be provided for each treatment group. All tabulations will be based on pooled data across centers.

All statistical tests will be two-sided and tested at the 5% level of significance.

Unscheduled visits will be excluded from the summaries but will be included in the data listings.

All p-values will be displayed to four decimal places, with p-values less than 0.0001 presented as '<0.0001'. Minimum and maximum values will be reported in the units of collection with 3 decimals being maximum value; the mean will be presented with 1 decimal place more and the standard deviation 2 decimal places more than the units of collection. Percentages for categorical summaries will be represented to 1 decimal place.

Analyses will be performed using SAS for Windows statistical software, version 9.4 or higher (SAS, Cary, NC), except where other software may be deemed more appropriate. In the event that other software is used to perform some analyses, the details will be provided in the Clinical Study Report.

will perform all efficacy and safety analyses described in this SAP and Grifols will review them.

Subject data will be listed, sorted by treatment group and subject number. When applicable, listings will be additionally sorted by visit and assessment date/time.

## 4.1 Analysis Quality Control Procedures

Once all the source verification is complete, all queries are resolved, and the database has been updated appropriately, the database will be locked and made available to Biostatistics for final analysis.

Data may be pulled by Biostatistics for the DSMB and interim futility analyses at a time when source verification and query resolution is ongoing.

All SAS programs used to create analysis data sets, tables, and listings are double programmed. The SAS outputs will be compared and the programs will be updated until the outputs match.

### 4.2 Analysis Populations

The following four analysis populations will be defined for this study:

The intent-to-treat (ITT) population is defined as all subjects who are randomized.

The modified intent-to-treat (mITT) population is defined as the subset of subjects included in the ITT who are also dosed. The mITT population will be used for all efficacy analyses. As sensitivity analysis, the primary efficacy analysis will also be carried out using the ITT population if different from the mITT population.

The Per-Protocol (PP) population is defined as the subset of subjects included in the mITT population who do not present major protocol violations which might have an impact on the primary efficacy endpoint(s), and complete at least 80% of the IP. The primary efficacy analyses will be carried out using the PP population if different from the mITT population.

The Safety (SAF) population is defined as subjects who receive at least any amount of blinded C19-IG 20%/Placebo. All safety analyses will be carried out using the SAF population based on the treatment actually received rather than randomized treatment.

The validity of a subject for inclusion in each of these populations (ITT, mITT, Safety, and PP) will be assessed before unblinding the database and documented in a blinded review report.

#### 4.3 Assessment Windows

Data will be summarized by nominal study visit recorded in the database.

### 4.4 Handling of Dropouts or Missing Data

Missing data will be treated as missing and no method for imputation is planned for study population or safety analyses except for the partial end dates/times for concomitant medications (Section 5.6) and partial onset dates/times for AEs (Section 7.2.1). When applicable, missing data for binary and selected continuous efficacy endpoints will be imputed using a most conservative/worst case approach, and the related details are described in Section 6.

Missing data on the time to event endpoints will have events coded as right censored per the

following table:

Endpoint	Right Censoring
Time to negative SARS-CoV-2 by PCR	Subjects who did not have negative SARS-CoV-2 by PCR will be right censored as of the date of last non-missing assessment of SARS-CoV-2 by PCR on or prior to Day 29.
Time to Clinical Progression (death, invasive mechanical ventilation, or ICU admission/requiring ICU level of care)	Subjects who did not meet the criteria for clinical progression will be right censored as of the date of last subject contact on or prior to Day 29.
Time to COVID-19 symptoms (fulfillment of the case definition used for the primary efficacy variable through Day 14)	Subjects who did not meet the criteria will be right censored as of the date of last non-missing assessment of clinical features/symptoms on or prior to Day 14.

#### 4.5 Multiple Comparisons

A hierarchical ordered testing procedure will be employed for handling the multiplicity issue to maintain the overall family-wised alpha level at 0.05 for comparisons between each dose and placebo. The null hypothesis for 1g vs placebo is tested only if the superiority for the 2g dose compared to placebo has been shown at a two-sided significance level of 5%. The order in which the null hypotheses are tested for the primary endpoint is predetermined as below:

- 1. Ho1: no difference between 2g and placebo on primary efficacy endpoint
- 2. Ho2: no difference between 1g and placebo on primary efficacy endpoint

The primary efficacy analysis will be carried out on the mITT population and repeated on the ITT and PP population (if different from the mITT population).

There will be no adjustment for multiple comparisons on secondary and exploratory efficacy endpoints.

#### 4.6 Data Derivations and Transformations

The following derivations will be used in this study:

Study Day:

- Date of assessment date of study drug administration + 1 for assessments done on or after date of study drug administration
- Date of assessment date of study drug administration for assessments done before date of study drug administration

Baseline Observation: the last non-missing value prior to study drug administration.

Duration:

• Duration in days = end date - start date + 1

• Duration in minutes = end time in minutes – start time in minutes

Origin or Start Date for Time to Event Endpoints:

- Time to negative SARS-CoV-2 by PCR: date of study drug administration
- Time to Clinical Progression: date of study drug administration
- Time to COVID-19 symptoms through Day 14: date of study drug administration

Event Date for Time to negative SARS-CoV-2 by PCR:

• The date of the first negative result from the SARS-CoV-2 assessment by PCR will be used as the event date for deriving time to negative SARS-CoV-2.

Event Date for Time to Clinical Progression

• The event date will be the date of death, the start date of invasive mechanical ventilation, or the date of ICU admission/requiring ICU level of care, whichever occurs first.

Event Date for Time to COVID-19 symptoms through Day 14

• The event date will be the first time point when any element of the case definition for primary efficacy variable is fulfilled through Day 14

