#### Diagnosis and Main Criteria for Eligibility

#### Inclusion Criteria:

A subject must meet all the following inclusion criteria to be eligible for participation in this study:

- 1. Ambulatory male or female outpatients ≥ 18 years of age who have laboratory-confirmed SARS-CoV-2 infection as determined by qualitative PCR (RT-PCR), or other commercial or public health assay approved by regulatory authorities as a diagnostic test for COVID-19 (inclusive of SARS-CoV-2 antigen testing or other approved rapid testing platforms) in any specimen ≤ 5 days prior to randomized treatment. (Note: ≤ 5 days is the post-sampling timeframe from date specimen obtained to administration of blinded study drug).
  - Note: Every effort should be made to reduce this time interval to the minimum as nearly immediate treatment is key for successful intervention. For instance, if SARS-CoV-2 antigen testing is used for diagnostic purposes the subject may be able to receive the study drug the same day testing is performed.
- 2. Asymptomatic with no constitutional COVID-19 illness (evident symptoms), specifically no fever, cough, shortness of breath, fatigue, anorexia, vomiting/diarrhea, headache that is unrelated to pre-existing medical conditions (eg, migraine), sore throat that is unrelated to other pre-existing medical conditions (eg, allergies, gastroesophageal reflux disease), myalgias, olfactory disorders unrelated with previous medical condition, or evidence of pneumonia at Screening.
- 3. Pulse oximetry SpO2 (oxygen saturation) on room air > 94% (i.e., 95% to 100%) at Screening.
- 4. National Early Warning Score (NEWS)  $\leq$  2 points (Appendix 2) at Screening.
- 5. Subject provides informed consent (informed consent form [ICF]) prior to initiation of any study procedures.

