### 6.2 Secondary Efficacy Endpoints and Analyses

### Change in SARS-CoV-2 viral load

Change in SARS-CoV-2 viral load (log10 copies/mL) from Baseline to Day 7 and to Day 14 will be compared between each C19-IG 20% dose group and placebo using the analysis of covariance (ANCOVA) model, including the change from baseline value as a dependent variable; treatment group as a fixed effect; and baseline SARS-CoV-2 viral load value, age and gender as covariates. From this model, the LS means and 95% CIs for each treatment group, the treatment difference in the LS means, the 95% CI for the difference, and the associated p-value will be presented at Day 7 and Day 14.

Subgroup analyses based on the presence of comorbidities associated with increased risk of serious

COVID-19 will be performed on change in SARS-CoV-2 viral load using the method described above with ANCOVA model at Day 7 and Day 14. If data permit, a subgroup analysis based on the number of comorbidities (<2 comorbidities vs. >=2 comorbidities) will also be performed.

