## Proportion of subjects remain in an outpatient setting and maintain SpO2 >94%

Subjects remain in an outpatient setting is defined as no hospitalization or ICU admission through Day 3, Day 7, and Day 14.

In the case when multiple  $SpO_2$  values are recorded on the same day, e.g.  $SpO_2$  values from subject self-reported at home and from healthcare provider visit on the same day, the lower value will be used for the analysis.

The proportion of subjects who remain in an outpatient setting and maintain  $\text{SpO}_2 \ge 94\%$  on room air at each timepoint within each treatment group will be presented along with a two-sided exact (Clopper-Pearson) 95% CI.

The observed difference in the proportion of subjects who remain in an outpatient setting and maintain  $\text{SpO}_2 \ge 94\%$  on room air at any timepoint between each C19-IG 20% dose group and placebo along with the exact unconditional 95% CI for risk difference will be calculated. The null hypothesis will be tested using Chi-square statistic and the p-value will be reported.

### Proportion of subjects negative for SARS-CoV-2 by PCR through Day 14 and Day 29

The proportion of subjects with negative SARS-CoV-2 by PCR through Day 14 and Day 29 within each treatment group will be presented along with a two-sided exact (Clopper-Pearson) 95% CI.

At each time point, the observed difference in the proportion of subjects with negative PCR test results between each C19-IG 20% dose group and placebo along with the exact unconditional 95% CI for risk difference will be calculated. The null hypothesis will be tested using Chi-square statistic and the p-value will be reported.

### Time to negative SARS-CoV-2 PCR from Baseline through Day 29

The time from baseline to the first occurrence of negative SARS-CoV-2 by PCR through Day 29 will be estimated using the Kaplan-Meier (KM) method. The KM estimates along with 95% CI, and survival curves will be provided. Based on the KM estimates, the probabilities of achieving negative SARS-CoV-2 by PCR and associated 95% CIs on Days 14 and 29 will be reported; in addition, the 25th, 50th (median), and 75th percentiles of the time to negative SARS-CoV-2 by PCR with associated 95% CIs will be provided, as data permit. The survival rates between each C19-IG 20% dose group and placebo will be compared using Log-rank test. The p-value from Log-rank test will be presented.

### Proportion of subjects requiring O2 supplementation on or before Day 29

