#### **Table 2 Sample Size Estimation**

[Sample sizes in table were calculated using https://www.sealedenvelope.com/power/binary-superiority/]

Based on the above extrapolation/estimate, and allowing for a total of 3 arms, randomized 1:1:1 to Placebo and 2 dose levels of C19-IG 20% approximately 801 subjects are allowed to be randomized as part of a humanitarian effort against COVID-19. N=267 subjects per group should allow differentiation in disease evolution for patients randomized to C19-IG 20% versus the control Placebo arm.

Sample size estimation was also calculated with regard to consideration of the viral load first secondary endpoint. A sample size of ~172 patients/arm would theoretically provide the trial with 80% power to detect a difference of 0.5 log10 in the mean reduction of SARS-CoV-2 viral load at a two-sided significance level of  $\alpha = 0.025$ , assuming an expected standard deviation of 1.5 . A 0.5 log10 copies/mL difference in reduction was chosen to represent the minimal threshold for a

biologically relevant change for analyses based on analogy with other viruses. However, it is unknown whether this degree of viral load reduction will be realized as a result of the planned dosages of C19-IG 20% within this clinical setting. The larger sample size per arm provides a greater level of assurance in this regard.

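### Subjects already PCR-negative on the pre-dose Day 1 swab stay in the viral-clearance and viral-load analyses, which dilutes the estimated effects on these secondary endpoints

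*SAP*

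**What the plan says.** Entry (Protocol 5.1 and synopsis, inclusion criterion 1) needs a positive result from any approved assay, "inclusive of SARS-CoV-2 antigen testing or other approved rapid testing platforms", on a specimen taken up to 5 days before dosing. A positive Day 1 swab is not required. A separate quantitative nasopharyngeal swab goes to the central laboratory on Day 1 before infusion, then on Days 3, 7, 14 and 29 (Protocol 4.2). Viral-load results are withheld from the investigator and blinded staff (Protocol 4.3.3), so the Day 1 swab cannot screen anyone out.

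All efficacy analyses use mITT, meaning randomised and dosed (SAP 4.2 and 6). The clock for time to negative starts on the dosing date, and "The date of the first negative result from the SARS-CoV-2 assessment by PCR will be used as the event date" (SAP 4.6). SAP 6.2 describes the quantity estimated by Kaplan-Meier as "The time from baseline to the first occurrence of negative SARS-CoV-2 by PCR through Day 29". Only subjects with no negative result are censored (SAP 4.4). Proportion negative is compared by chi-square with no baseline condition. Change in viral load is analysed by ANCOVA with "baseline SARS-CoV-2 viral load value, age and gender as covariates" (SAP 6.2).

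The documents give no rule for a negative Day 1 swab, no value for results below the detection limit, and no sensitivity analysis on this point.

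**The concern.** A subject who is negative before dosing supplies a clearance event that treatment did not cause. Read literally, SAP 4.6 places that event on Day 1. If only post-dose swabs count, it typically falls at Day 3, the next swab. Two programmers could follow the text and produce different Kaplan-Meier curves. A Day 1 negative who later turns positive would, on the literal reading, still be recorded as cleared on Day 1.

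For viral load, such a subject has no measurable quantity to fall and pulls the mean difference towards zero.

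At stake are the estimates, and to a varying degree the power, for three related secondary endpoints. Viral load is the first secondary endpoint and has its own sample-size calculation in SAP 10.

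**Working it through.** **Inputs from the documents.** SAP 10: "A sample size of ~172 patients/arm" "would theoretically provide the trial with 80% power to detect a difference of 0.5" log10, "assuming an expected standard deviation of 1.5", at two-sided 0.025; 267 randomised per arm with 10% withdrawal, so 267 × 0.9 ≈ 240 evaluable. SAP 4: tests at two-sided 0.05. Swab days: 3, 7, 14 and 29.

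**Assumptions.** The share q negative on the Day 1 central swab is taken as 5% to 30%. Treatment is taken not to change the outcome of those subjects. For time to negative, the hazard ratio is 1.35 and the placebo median is 12 days (exponential) among those positive at Day 1, observed on the swab days.

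**1. The plan's own figure.** n = 2 × 1.5² × (2.241 + 0.842)² / 0.5² = 171.1, rounded up to 172 per arm. This matches SAP 10.

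**2. Viral load, unadjusted.** If Day 1 negatives are kept, the expected difference is D = 0.5 × (1 − q), and power = Φ(D / (1.5 × √(2/n)) − 1.96) with n = 240. If they are excluded, the difference is 0.5 and n = 240 × (1 − q). At q = 20%:
- kept: 0.40 / 0.1369 − 1.96 = 0.96, power 83.2%
- excluded (n = 192): 0.50 / 0.1531 − 1.96 = 1.31, power 90.4%

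| q | Difference if kept | Power, kept | Power, excluded |
|---|---|---|---|
| 0 | 0.50 | 95.5% | 95.5% |
| 5% | 0.475 | 93.4% | 94.5% |
| 10% | 0.45 | 90.8% | 93.4% |
| 20% | 0.40 | 83.2% | 90.4% |
| 30% | 0.35 | 72.4% | 86.3% |

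**3. Viral load, with the planned ANCOVA.** Step 2 holds the SD at 1.5 in the mixed group. If Day 1 negatives add no variance and baseline load absorbs their different mean change, the SD becomes 1.5 × √(1 − q). Then D/SD = (0.5/1.5) × √(1 − q), which is exactly the restricted analysis, so the power difference is nil. A simulation with near-zero load and a change SD of 0.3 in the negatives gave 92.7%, 88.6% and 84.9% kept, against 93.6%, 90.2% and 86.1% excluded, at q = 10%, 20% and 30%. That is a gain of 1 to 2 points.

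A different simulation had a fall in positives that did not depend on baseline load, so a linear covariate absorbed little. At q = 20%, 172 per arm and two-sided 0.025 it gave 59% kept against 71% excluded. In that simulation the estimate was about 0.41 if negatives were kept and 0.51 if they were excluded. The covariate can recover power but does not restore the estimate.

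**4. Time to negative, simulated log-rank power** (240 per arm, two-sided 0.05).

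| q | Kept, event Day 1 | Kept, event Day 3 | Excluded |
|---|---|---|---|
| 0 | 83% | 83% | 83% |
| 5% | 78–81% (both readings) | | about 83% |
| 10% | 72% | 74% | 80% |
| 20% | 61% | 66% | 76% |
| 30% | 52% | 56% | 69% |

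A second clearance pattern (placebo 10/30/60/90% cleared by Days 3/7/14/29, same hazard ratio, 85% power at q = 0) gave 75/60/49% kept and 81/76/69% excluded at q = 10/20/30%. With 2,000 trials per setting in the table, simulation error is about √(0.6 × 0.4 / 2000) = 1 point.

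**5. Proportion negative at Day 14.** Under the model in step 4, a difference of about 11 points shrinks to 9.7, 8.9 and 7.8 points at q = 10%, 20% and 30%.

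**The case against.** **The share may be small.** Protocol 2 reports a median of 20.0 days of RNA detection (IQR 17.0–24.0) in survivors, and entry requires a positive specimen no more than 5 days old. The cited cohort is one of adult inpatients, so transfer to asymptomatic outpatients is uncertain, but the figure points to a low share. At 5% the viral-load effect is negligible (93.4% against 94.5% power). This stands as a limit on size. It does not settle how a Day 1 negative is to be counted.

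**Baseline load is already in the ANCOVA.** This largely stands for power if the covariate absorbs these subjects (step 3). It does not stand for the estimate, and the log-rank and chi-square analyses have no such covariate.

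**A full-mITT analysis is a legitimate target:** the effect in everyone treated on the entry test. True, and it should still be reported.

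Four stronger readings are tempting, and the documents do not support them:
- That the plan certainly scores these subjects at time zero. The wording allows it, but counting from the first post-dose swab is also a natural reading.
- That treatment cannot affect them at all. A Day 1 negative may be a sampling miss or an early low load, with later positive swabs.
- That viral-load power falls from 95% to 83% at a 20% share and restriction would recover the loss. Restriction also reduces n, so the unadjusted gain is about 7 points, and 0 to 2 points if the ANCOVA absorbs these subjects.
- That a false-positive finding becomes more likely. Randomisation balances the share across arms, so the pull is towards no difference.

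**Conclusion.** The gap is confirmed from the text, and so is its direction: the estimated effects on time to negative, proportion negative and viral load are diluted according to the share who are negative before dosing. The size is conditional on that share, which the documents do not give, and on the assumed hazard ratio and clearance pattern.

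Over shares of 5% to 30%, the log-rank loss from keeping these subjects rather than excluding them runs from a few points to about 15–20. The viral-load estimate shrinks by the share itself, while the power recoverable by restriction is small to moderate and depends on the model.

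The consequence is limited. These are secondary endpoints without multiplicity adjustment (SAP 4.5). They are absent from the futility list in SAP 9, and neither the primary test nor type I error is affected. The change is worthwhile because it is cheap, not because a confirmatory conclusion depends on it.

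**What to change.** Before unblinding, amend SAP 4.2, 4.6 and 6.2 for these three endpoints:
- Make mITT subjects with a positive, quantifiable Day 1 central PCR the main analysis set.
- Count only negatives from swabs taken after dosing as events.
- State the value given to results below the detection limit.
- Report the share negative on Day 1 by arm, and the full-mITT result as supportive.

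The cost is SAP wording and one derived flag; no new data are needed. The set is defined by a pre-dose value, so the randomised comparison is preserved. The downside is a smaller analysis set, by the factor (1 − q). At a 20% share that is 240 × 0.8 = 192 per arm, so restriction restores the estimate but not all of the planned power.
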